The relationship between immune infiltrates and MSI-H in CRC is well established. Immunotherapy with anti-PD1 therapy may have efficacy in this population. Nivolumab and ipilumumab was well tolerated with a response rate of 33% in metastatic MSI-H CRC. TGF $\beta$ , being a central determinant of an immune suppressive TME may be a key resistance mechanism in PDL1 therapy strategies. It does so both directly on T cells to differentiate into Tregs or indirectly via attraction of immunosuppressive immature myeloid and MDSCs into the TME. Upregulation of TGF- $\beta$  signaling has been associated with de novo resistance to anti-PD-1 treatment in patients with metastatic melanoma and following development of acquired resistance to these agents following an initial response to therapy. Given the ability of M7824 to sequester TGF- $\beta$  in the circulation away from the TME, we hypothesize that M7824 may promote T cell effector function via disruption of PD-1/PD-L1 axis to enhance anti-tumor response following resistance to anti-PD-1/PD-L1 therapy in patients with MSI-H mCRC.

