### **3.2** Secondary Objectives

To estimate progression-free survival (PFS) for M7824 in patients with:

• MSI-H solid tumors whose disease has progressed on prior immune checkpoint blockade therapy (Cohort A-C).

OR

Treatment-refractory, CMS4 mCRC coadministered SBRT (Cohort B). While SBRT is preferred, IMRT or 3D conformal techniques may be utilized at the discretion of the treating radiation oncologist depending on the dose to surrounding normal tissues. Patient will receive a total dose of 24Gy over three days with one of the following modalities, at the discretion of the treating radiation oncologist: SBRT, IMRT and 3D conformal.

To estimate overall survival (OS) for M7824 in patients with:

• MSI-H solid tumors who are refractory to prior immune checkpoint blockade therapy (Cohort A-C).

OR

Treatment-refractory, CMS4 mCRC coadministered SBRT (Cohort B). While SBRT is preferred, IMRT or 3D conformal techniques may be utilized at the discretion of the treating radiation oncologist depending on the dose to surrounding normal tissues. Patient will receive a total dose of 24Gy over three days with one of the following modalities, at the discretion of the treating radiation oncologist: SBRT, IMRT and 3D conformal.

OR

ctDNA(+) resected mCRC following completion of standard-of-care therapy (Cohort D).

To estimate disease-free survival (DFS) in patients with resected mCRC following standard-of-care treatment (cohort D).

To evaluate safety and tolerability of treatment with M7824 in patients with:

• MSI-H mCRC who are refractory to prior immune checkpoint blockade therapy (Cohort A-C).

OR

• Treatment-refractory, CMS4 mCRC (Cohort B)

OR

.

ctDNA(+) resected mCRC following completion of standard-of-care therapy (Cohort D).

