#### 4 Investigational Plan

#### 4.1 Overall Trial Design and Plan

#### 4.1.1.1 Cohort A-C – MSI-H solid tumors

This is a phase Ib expansion study to assess efficacy of M7824 in patients with MSI-H solid tumors who have progressed on prior anti-PD-1/PD-L1 therapy. The hypothesis is that these patients will demonstrate anti-tumor response upon treatment with M7824. Patients successfully enrolled will have had at least two doses of prior immune checkpoint therapy (anti-PD1, anti-PDL1 or anti-CTLA4) with documented progression on CT or MRI imaging.

M7824 will be administered intravenously at a dose of 1200mg every 14 days (-3/+1 day). M7824 will be administered until documented PD, unacceptable toxicity, or withdrawal of informed consent. Tumor assessments will be performed every 8 weeks. Progressive disease, stable disease, partial response, and complete response will be defined by iRECIST 1.1. Patients who discontinue due to toxicity will continue to be assessed via imaging until documented PD.

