## 4.3 Selection of Trial Population

### 4.3.1 Inclusion criteria

- 1. Histologically or cytologically confirmed adenocarcinoma of the colon or the rectum that is metastatic or unresectable (cohort B); or histologically or cytologically confirmed adenocarcinoma of the colon or the rectum following resection of the primary tumor and metastatic disease, following completion of standard-of-care perioperative therapy at the discretion of the treating provider (cohort D).
- 2. Confirmation of:
  - a. Cohort A-C: microsatellite instability
  - b. Cohort B: CMS4 CRC classification on pretreatment primary tumor.
  - c. Cohort D: microsatellite stability
- 3. Age >18 years at time of study entry.
- 4. Ability to provide written informed consent.
- 5. Documented progression to prior therapies (Cohorts A-C and B):
  - a. Cohort A-C: Disease progression following prior immune checkpoint blockade therapy
  - b. Cohort B: Progression or intolerance to at least 2 prior lines of standard therapy for unresectable or metastatic CRC
- 6. Available primary tumor tissue for CMS4 biomarker assessment (cohort B)
- 7. Life expectancy  $\geq 12$  weeks as judged by the treating physician.
- 8. Eastern Cooperative Oncology Group (ECOG) performance status of 0 or 1.
- 9. Measurable disease according to iRECIST v1.1 (Cohorts A-C and B). For cohort B, measureable lesions must be identified apart from the irradiated tumor lesion. Patients in cohort D must have no evidence of radiographically evident disease at the time of study entry.
- 10. Adequate hematological function, defined by ANC  $\geq 1.0 \times 10^{9}$ /L, lymphocyte count  $\geq 0.5 \times 10^{9}$ /L, platelet count  $\geq 100 \times 10^{9}$ /L, and Hgb  $\geq 9$  g/dL (in absence of blood transfusion).
- Adequate hepatic function defined by a total bilirubin level ≤ 1.5 × the upper limit of normal (ULN), an AST level ≤ 2.5 × ULN, and an ALT level ≤ 2.5 × ULN. If liver metastases are present, then it is acceptable for AST level ≤ 5.0 × ULN, and an ALT level ≤ 5.0 × ULN.
- 12. International normalized ratio (INR) < 1.5
- 13. Adequate renal function defined by an estimated creatinine clearance >30 mL/min according to the Cockcroft-Gault formula or be measure for creatinine clearance from 24 hour urine collection.

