#### 4.5.1.1 Pseudoprogression

Pseudoprogression is defined as an initial disease flare followed by a delayed disease response. At the time of progression, there is no definitive way to distinguish this from true progressive disease without a confirmatory scan.

To account for pseudoprogression, patients will have PD, SD, PR or CR recorded as defined by iRECIST 1.1. However, PD will require a subsequent scan at the next planned tumor assessment in 8 weeks or earlier if clinically indicated. Patients will be allowed to continue on M7824 despite first documentation of PD if:

- No new Grade 2 or greater severity of symptoms or significant worsening of existing symptoms
- No decrease in ECOG PS
- In the opinion of the Investigator, the subject does not require new anticancer therapy.

Failure to satisfy **all** of these conditions results in discontinuation of M7824.

Confirmed PD on the subsequent scan also results in study discontinuation.

The time point for PD will be taken from the first noted date and not the time of the confirmation scan.

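### Cohort A-C's entry rules are wider than its stated population: anti-CTLA-4-only and off-treatment-relapse patients can enter a pooled ORR meant to show activity after anti-PD-1/PD-L1 resistance

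*Combined protocol and SAP*

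**What the plan says.** Section 2.2.5 states the hypothesis as activity "following resistance to anti-PD-1/PD-L1 therapy in patients with MSI-H mCRC". Section 4.1.1.1 opens with "patients with MSI-H solid tumors who have progressed on prior anti-PD-1/PD-L1 therapy". The same paragraph then describes enrolled patients as having had "at least two doses of prior immune checkpoint therapy (anti-PD1, anti-PDL1 or anti-CTLA4) with documented progression on CT or MRI imaging".

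Criterion 5a in Section 4.3.1 reads "Cohort A-C: Disease progression following prior immune checkpoint blockade therapy". It stands under a criterion heading that calls for documented progression. It names no agent class and does not require progression during treatment. Section 4.4 makes the inclusion and exclusion lists the check before enrolment.

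The wording varies elsewhere. Section 3.1 and Section 2.2.6.7 speak of progression *on* checkpoint therapy of unspecified class. Section 3.2 uses *on* for PFS and *refractory* for OS and safety, without defining the latter. Section 4.2.1.1 opens with *on*, but later in its justification uses *following*.

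Section 7.5.2.1.1 defines ORR as responders over all treated patients. Section 7 sets no null rate for this cohort and no split by prior agent or type of progression.

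**The concern.** M7824 has an active PD-L1 component. Section 2.1 describes it as avelumab apart from a few amino-acid substitutions. In a patient whose tumour is still sensitive to PD-1/PD-L1 blockade, that component alone could produce a response, whatever the TGF-beta trap adds. Section 4.2.1.1 relies on prior progression to make sure that a resistance mechanism is being targeted, and this works only if the prior progression shows resistance to the same axis.

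Two kinds of patient fit the entry wording without showing it:

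- A patient treated only with anti-CTLA-4 meets both Section 4.1.1.1 and criterion 5a, but is naive to the axis.
- A patient who stopped anti-PD-1 while benefiting and relapsed later has progressed *following* checkpoint blockade, and so meets criterion 5a, but has not progressed *on* it.

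With 15 patients, no comparator and a pooled rate, a response in either patient would be read as activity after resistance.

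**Working it through.** **1. The passages side by side.**

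| Place | Prior agent | Relation to treatment |
|---|---|---|
| 2.2.5 | anti-PD-1/PD-L1 | resistance |
| 4.1.1.1, first sentence | anti-PD-1/PD-L1 | progressed on |
| 4.1.1.1, qualifier | anti-PD-1, anti-PD-L1 or anti-CTLA-4, at least two doses | progression documented on CT/MRI |
| 4.3.1, criterion 5a | any checkpoint blockade | following |
| 3.1 | any checkpoint blockade | progressed on |
| 3.2 | any checkpoint blockade | progressed on (PFS); refractory (OS, safety) |

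The anti-CTLA-4 route is explicit in Section 4.1.1.1 and is not closed by criterion 5a. The late-relapse route comes from the word *following* in criterion 5a, against *on* in most other places. The only Cohort A-C exclusion tied to prior checkpoint therapy (Section 4.3.2, item 5) concerns intolerance and immune-related events. It leaves both routes open.

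**2. The plan's own figure.** Section 7.1 gives a maximum 95% half-width of 0.253 for 15 patients. The normal approximation gives 1.96 × √(0.5 × 0.5 / 15) = 0.253, so the figure reproduces. The exact interval named in Section 7.5.2.1.1 has a maximum half-width of 0.261. Neither figure depends on this point.

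**3. Illustration of the shift.** Inputs:

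- n = 15 (Sections 4.1.2.1 and 7.1).
- q = response rate in axis-naive MSI-H patients, 31% to 53%. These are the lowest and highest anti-PD-1 rates quoted in Sections 2.2.6.7 and 4.2.1.1. *Assumption:* they apply to the PD-L1 component of M7824.
- r = true ORR in resistant patients. Not given; *assumed* 5% or 10%.
- k = number of axis-naive patients. Not given; *assumed* 1 to 3.

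Expected ORR = ((15 − k) × r + k × q) / 15.

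| k | r = 5%, q = 31% | r = 5%, q = 53% | r = 10%, q = 31% | r = 10%, q = 53% |
|---|---|---|---|---|
| 1 | 6.7% | 8.2% | 11.4% | 12.9% |
| 2 | 8.5% | 11.4% | 12.8% | 15.7% |
| 3 | 10.2% | 14.6% | 14.2% | 18.6% |

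Examples: (14 × 0.10 + 1 × 0.31) / 15 = 1.71 / 15 = 11.4%; (12 × 0.05 + 3 × 0.53) / 15 = 2.19 / 15 = 14.6%.

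The shift is (k / 15) × (q − r). It runs from (1/15) × 0.21 = 1.4 points to (3/15) × 0.48 = 9.6 points. The largest shift equals 0.096 × 15 = 1.4 responders.

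No such calculation is possible for late-relapse patients, because the documents give no response rate on re-treatment.

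**The case against.** **No decision rule depends on it.** Cohort A-C is a descriptive Phase Ib cohort with no null rate and no efficacy threshold. The shifts above lie well inside the stated half-width of 25.3 points. Section 3.1 asks for an estimate of the efficacy of M7824, not for attribution to TGF-beta trapping. This stands and limits the severity. It does not remove the point: a wide interval expresses sampling error, not uncertainty about which population was sampled.

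**The frequency may be close to nil.** The only anti-CTLA-4 use in MSI-H disease that the documents describe is in combination with nivolumab (Section 2.2.5), and such patients are not axis-naive. The trial runs in one department of one centre (Section 1), where a consistent reading is more likely. This also stands, and is why the figures are only an illustration.

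**The data allow a later look.** Prior immunotherapy is recorded (Section 6.2.2) and all data are listed individually (Section 7.5.1). That helps, but an unplanned split of 15 patients does not restore the intended sample.

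A reader might also infer more than the documents support:

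- *That MSI-L patients can enter, because criterion 2a says only microsatellite instability.* Section 2.2.6.7 selects on MSI-H status, and Section 6.4.5 requires documented MSI-H for external results.
- *That a patient with one prior dose, or no imaging, can enter.* Section 4.1.1.1 requires at least two doses and CT/MRI progression.
- *That every qualifying progression must be confirmed by a second scan.* Section 4.5.1.1 does say of on-study progression that "there is no definitive way to distinguish this from true progressive disease without a confirmatory scan". But the screening scan is waived when one from the previous 4 weeks exists (Table 1, footnote i; Section 6.2.5), so confirmation could need an extra procedure. It is not asked for here.
- *That the ORR will be overstated two- to three-fold.* That needs three axis-naive patients of 15 and a true rate of 5% together, and neither figure has a source in the documents.

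**Conclusion.** The inconsistency is real. The hypothesis and the opening of Section 4.1.1.1 define the cohort by anti-PD-1/PD-L1 progression, while the qualifier in the same section and criterion 5a admit patients who have not shown it. The pooled ORR cannot tell the two groups apart.

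The size of any effect is unknown. The illustrated ranges rest on three assumptions: the number of axis-naive patients, the true rate in resistant patients, and the transfer of anti-PD-1 response rates to the PD-L1 component. No sample-size or precision figure in the plan is wrong because of this.

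Severity is moderate. The documents do not support calling the cohort uninterpretable or the point a must-fix, since the analysis is descriptive and no rule turns on the result.

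**What to change.** 1. Reconcile Section 4.1.1.1, criterion 5a and objectives 3.1 and 3.2 to one definition that fits the hypothesis: CT/MRI-documented progression on anti-PD-1 or anti-PD-L1 therapy, alone or in combination, after the at least two doses already stated in Section 4.1.1.1. Remove anti-CTLA-4 as a stand-alone qualifier, replace *following* with *on*, and say what counts as on treatment. The objectives must be amended too: they now name any checkpoint blockade, so changing criterion 5a alone would leave it narrower than the primary objective.
2. Prespecify in Section 7.5.2.1.1 a descriptive ORR by prior agent class and by on-treatment versus off-treatment progression. This also covers anyone enrolled under the present wording. Section 6.2.2 already records prior therapy; check that the case report form lets progression be placed relative to the last dose.

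The cost is protocol wording and one additional table. A few anti-CTLA-4-only or late-relapse patients would not be enrolled. The sample size and stated precision do not change, and no procedure is added. With 15 patients the split would be descriptive only.

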## 4.3.2 Exclusion criteria

- 1. Concurrent treatment with non-permitted drugs and other interventions.
- 2. Anticancer treatment within 14 days before the start of trial treatment [e.g., cytoreductive therapy, radiotherapy (with the exception of palliative radiotherapy delivered in a normal organ-sparing technique), immune therapy, or cytokine therapy].
- 3. Major surgery as determined by the investigator within 28 days before the start of trial treatment (prior diagnostic biopsy is permitted).
- 4. Systemic therapy with immunosuppressive agents within 7 days before the start of treatment; or use of any investigational drug within 28 days before the start of trial treatment.
- 5. Cohort A-C only: Intolerance or serious adverse immune related adverse events (irAEs) [refer to section 5.5.3.3] that were symptomatic or required or continues to require ongoing immunosuppression to previous immune checkpoint therapy.
- 6. Cohorts B and D: prior exposure to any immune checkpoint blockade agent or any other immunomodulatory agent used for antineoplastic therapy for mCRC.
- 7. Previous malignant disease (other than the target malignancy to be investigated in this trial) within 3 years prior to study treatment initiation. Other Lynch syndrome cancers do not exclude patients from participating on study, at the discretion of the Principal Investigator. Subjects with a history of cervical carcinoma in situ, superficial or non-invasive bladder cancer, or basal cell or squamous cell carcinoma in situ, previously treated with curative intent are NOT excluded. Subjects with other localized malignancies treated with curative intent need to be discussed with the Principal investigator.
- 8. Subjects with active central nervous system (CNS) metastases are excluded. Subjects with a history of treated CNS metastases (by surgery or radiation therapy) are not eligible unless they have fully recovered from treatment, demonstrated no progression for at least 2 months, and do not require continued steroid therapy.
- 9. Receipt of any organ transplantation, including allogeneic stem-cell transplantation, but with the exception of transplants that do not require immunosuppression (e.g., corneal transplant, hair transplant).
- 10. Significant acute or chronic infections including, among others:

- a. Known history of testing positive test for human immunodeficiency virus (HIV) or known acquired immunodeficiency syndrome.
- b. HBV or HCV infection (HBV surface antigen positive and HBV core antibody positive with reflex to positive HBV DNA or HBV core antibody positive alone with reflex to positive HBV DNA or positive HCV antibody with reflex to positive HCV RNA).
- c. Subjects with active tuberculosis (history of exposure or history of positive tuberculosis test plus presence of clinical symptoms, physical or radiographic findings).
- 11. Active autoimmune disease that might deteriorate when receiving an immunostimulatory agent:
  - a. Subjects with type I diabetes, vitiligo, alopecia, psoriasis, hypo- or hyperthyroid disease not requiring immunosuppressive treatment are eligible
  - b. Subjects requiring hormone replacement with corticosteroids are eligible if the steroids are administered only for the purpose of hormonal replacement and at doses  $\leq 10$ mg of prednisone or equivalent per day.
  - c. Administration of steroids for other conditions through a route known to result in a minimal systemic exposure (topical, intranasal, intro-ocular, or inhalation) is acceptable.
- 12. Known severe hypersensitivity reactions to monoclonal antibodies (Grade ≥ 3 NCI-CTCAE v4.03), any history of anaphylaxis, or recent (within 5 months) history of uncontrolled asthma.
- 13. Persisting toxicity (except alopecia and vitiligo) related to prior oncologic therapy Grade >1 NCI-CTCAE v4.03, however, sensory neuropathy Grade  $\leq 2$  is acceptable.
- 14. Clinically significant cardiovascular/ cerebrovascular disease as follows: cerebral vascular accident / stroke (<6 months prior to enrollment), myocardial infarction (<6 months prior to enrollment), unstable angina, congestive heart failure (New York Heart Association Classification Class >II), or serious cardiac arrhythmia.
- 15. Clinically relevant diseases (for example, inflammatory bowel disease) and / or uncontrolled medical conditions, which, in the opinion of the Investigator, might impair the subject's tolerance or ability to participate in the trial.
- 16. Vaccine administration within 4 weeks of M7824 administration. Vaccination with live vaccines while on trial is prohibited. Administration of inactivated vaccines is allowed (for example, inactivated influenza vaccines).
- 17. Cohort D: peritoneal carcinomatosis.

### 4.3.3 Screening Eligibility (cohort B)

Patients are eligible for screening for CMS subtyping prior to enrollment on cohort B provided that the following elibility criteria are met:

• Histologically or cytologically confirmed adenocarcinoma of the colon or the rectum that is metastatic or unresectable.

- Progression on at least one prior line of systemic therapy for metastatic disease.
- Prior tissue sampling of primary tumor with core biopsy, endoscopic biopsy, or surgical resection to be used for CMS subtype testing.

#### 4.4 Criteria for Initiation of Trial Treatment

The inclusion and exclusion criteria will be checked at the Screening visit. Eligible subjects will be enrolled before treatment start after verification of fulfilling all inclusion criteria and satisfy no exclusion criteria. Documentation of satisfaction of eligibility criteria for each patient will be performed within CORe.

### 4.5 Criteria for Subject Withdrawal

#### 4.5.1 Withdrawal from Trial Treatment

Subjects will be withdrawn from trial treatment for any of the following reasons:

- PD as defined by iRECIST 1.1
  - Patients may continue on M7824 until immune confirmed PD (iCPD) provided they meet the criteria for pseudoprogression (see 5.5.1.1 below)
- Therapeutic failure requiring urgent additional cancer therapy
- Occurrence of any Grade ≥ 3 ADRs or repetitive Grade 2 ADRs as defined in Section 5.5.3.3.
- Occurrence of AEs, at the Investigator's discretion
- Pregnancy
- Use of prohibited concomitant drug, as defined in Section 5.5.2, where the predefined consequence is withdrawal from the IMP
- Non-adherence / non-compliance to the trial protocol or trial requirements (see Section 5.9)
- Withdrawal of consent
- Participation in any other trial

#### 4.5.1.1 Pseudoprogression

Pseudoprogression is defined as an initial disease flare followed by a delayed disease response. At the time of progression, there is no definitive way to distinguish this from true progressive disease without a confirmatory scan.

To account for pseudoprogression, patients will have PD, SD, PR or CR recorded as defined by iRECIST 1.1. However, PD will require a subsequent scan at the next planned tumor assessment in 8 weeks or earlier if clinically indicated. Patients will be allowed to continue on M7824 despite first documentation of PD if:

- No new Grade 2 or greater severity of symptoms or significant worsening of existing symptoms
- No decrease in ECOG PS
- In the opinion of the Investigator, the subject does not require new anticancer therapy.

Failure to satisfy **all** of these conditions results in discontinuation of M7824.

Confirmed PD on the subsequent scan also results in study discontinuation.

The time point for PD will be taken from the first noted date and not the time of the confirmation scan.

### 4.5.2 Withdrawal from the Trial

Subjects may withdraw from the trial at any time without giving a reason. Withdrawal of consent will be considered withdrawal from the trial. If a subject withdraws participation while on study, survival information may still be collected via phone calls, electronic communication, letters or publically available records.

A subject must be withdrawn if any of the following occur during the trial:

- Withdrawal of the subject's consent
- Participation in any other therapeutic trial during the treatment duration of this trial; however, subjects will continue to be followed for survival

If a subject fails to attend scheduled trial assessments, the Investigator must determine the reasons and the circumstances as completely and accurately as possible.

In case of withdrawal from the trial, the assessments scheduled for the last visit (28-Day Safety Follow-up visit) should be performed (see Section 6.1.3), if possible, with focus on the most relevant assessments. In any case, the appropriate 28-Day Safety Follow-up electronic case report form (eCRF) in the Prometheus database visit must be completed. In case of withdrawal, subjects will be asked to continue safety and survival follow-up, which includes the collection of data on survival and subsequent anticancer therapy. After completion of the Follow-up period or after the End of Treatment visit, whatever is applicable, the appropriate eCRF section for Trial Termination must be completed in the Prometheus database.

If a subject is withdrawn prior to PD for any reason the subject will not be replaced.

